Real Time Assessment of Pre-oxygenation Utilizing End-tidal Oxygen Measurements versus Single Breath End-Tidal Oxygen Measurements in Healthy Volunteers

Short Title: Pre-oxygenation with Real Time End-tidal Oxygen Measurements versus Single Breath Measurements

Principal Investigator: [name]

Sponsors: None

Protocol Version 6  
March 20, 2025

NCT03840486

1. External (non-Emory) Collaborators: Not applicable
2. Precis/Abstract: A brief (usually 400 words or fewer) description of the study objectives, population, design, and outcome measures

Patients in the Emergency Department (ED) undergoing Rapid Sequence Intubation (RSI) are at risk for serious morbidity and mortality. In order to provide oxygen during the apneic period, it is common practice to provide pre-oxygenation prior to the start of the procedure with high flows of oxygen. Different methods of pre-oxygenation have been studied by taking a single breath end-tidal oxygen (EtO2) measurement with higher levels indicating more complete pre-oxygenation. However, there has not been any research examining methods of determining the quality of pre-oxygenation in real time.

This study examines the performance of a nasal cannula EtO2 measurement as compared to the gold standard of single breath end-tidal oxygen measurements in healthy volunteers. Study subjects will be placed on either a NRBM at different flow rates (15 LPM, 35 LPM, or Flush rate at 55 LPM) or a non-invasive ventilator facemask at various fractions of inspired oxygen levels (40%, 70% and 100%) for separate trials of 3 minutes at each flow rate or FiO2. At the end of each intervention, study subjects will perform a single breath end-tidal oxygen measurement by exhaling fully into a tube attached to an EtO2 sensor. In addition, a fourth trial arm will be done for both the NRBM and the NIV subjects that will correlate maximal readings from the real time EtO2 nasal cannula at the moment those maximal readings are obtained. The primary outcome will be the degree of correlation between real time EtO2 measurements (at the end of the three minute trial) and a single breath end-tidal oxygen measurement as measured by the k correlation coefficient, as measured for each trial. The secondary outcome will be the correlation of EtO2 between the nasal cannula sensor and the single breath sensor once stabilized at maximal readings.

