## **Introduction**

We hypothesize that end-tidal oxygen (EtO2) could be continuously and reliably measured using a nasal cannula with a gas sampling line that is typically used to measure end-tidal CO2 (EtCO2) during pre-oxygenation in healthy volunteers. However, it is possible that high flows of oxygen that would be typically required for pre-oxygenation could distort patient measurements when placed underneath the oxygen mask. To our knowledge, no studies have examined this technique.

Use of the EtO2 real time reading from a nasal cannula could lead to improved pre-oxygenation for ED patients undergoing RSI by allowing clinicians to gauge the completeness of pre-oxygenation prior to starting the intubation procedure. Clinically, if a patient has a low EtO2 or ORI reading, this could prompt clinicians to delay the procedure until the patient can be better pre-oxygenated. This could lead to improved patient safety by decreasing the incidence of hypoxia during the intubation procedure that can lead to significant morbidity and mortality. Conversely, if the EtO2 is already at 90% or greater, the clinician may be able to start the intubation procedure sooner and not delay other critical interventions while waiting to further pre-oxygenate the patient.

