### **4. Study design and methods:**

#### **Study Procedure**

After screening procedures, participants will be asked to self report age, gender, height, and weight. Each participant will then perform a single breath EtO2 measurement to determine their own individual room air EtO2 measurement. They will also have a baseline measurement taken by the EtO2 nasal cannula sensor. Subjects will then be fitted for an appropriately sized non-invasive ventilator mask. Prior to the start of the study procedure, a nasal cannula EtO2 sensor will be placed on the participant's face with the non-invasive mask overlying the sensor. Participants will be randomized into each study arm after enrollment: the NRBM arm and the

NIV arm. Each participant will participate in the following treatment sequence. In addition to the study arm allocation, participants will be randomized to the order of their treatment sequence. After each treatment is completed, the participant will perform a single breath exhalation into a standard FeO2 sensor.

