**Group 1: NRBm Arm**

#1 NRBm at 15 LPM for 3 minutes

#2 NRBm at 35 LPM for 3 minutes

#3 NRBm at flush rate (55 LPM) for 3 minutes, the maximal reading at the end of this trial will be recorded, then the study subject will be allowed to rest until their EtO2 returns to their baseline, then they will be placed back on NRBm at flush rate, allowed to rise to the maximal reading of the previous step, then do a single breath exhaled EtO2 measurement

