## **Data collection and storage procedures**

All data will be collected on a standardized data collection form and entered into a secure database program (REDCAP) for data analysis. The PI, AI, and any study research personnel who assist with the study will have access to the database. Each subject will be assigned a subject number according to the order in which they were enrolled into the study. The data will be stored for a maximum of 3 years to ensure the ability to publish study results. After the data is stored for 3 years, it will be deleted. In addition, the study investigators will video record the screens displaying the EtO2 data to allow accurate data transcription. Once the data has been transcribed, these videos will be deleted. These videos will solely be focused on the video screen and will not capture the study subject’s face or any other identifying features. These videos will only be identified by the assigned study subject number and will not contain any other identifying information.

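### No cannula/reference pair on oxygen is scheduled during the rise, so the trial cannot support a claim that the cannula is accurate there

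*Combined protocol and SAP*

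**What the plan says.** The primary outcome in section 2 (Precis/Abstract) pairs real-time EtO2 "measurements (at the end of the three minute trial) and a single breath end-tidal oxygen measurement" and is a correlation coefficient calculated for each trial. The secondary outcome is the correlation "between the nasal cannula sensor and the single breath sensor once stabilized at maximal readings". In condition #3 of each arm the volunteer rests to baseline, goes back on oxygen and is "allowed to rise to the maximal reading of the previous step, then do a single breath exhaled" EtO2 measurement (Group 1: NRBm Arm; Group 2: NIV arm has the same step). No clock time is set for that breath.

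The other planned pair is on room air. Study Procedure has a baseline single breath and adds: "They will also have a baseline measurement taken by the" cannula sensor. No mask oxygen is flowing then.

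The Introduction says it is possible that "high flows of oxygen that would be typically required for pre-oxygenation could distort patient measurements when placed underneath the oxygen mask". It also describes a use: if the reading is already 90% or more, "the clinician may be able to start the intubation procedure sooner and not delay other critical interventions".

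Under Data collection and storage procedures, "the study investigators will video record the screens displaying the" EtO2 data. Under Confidentiality, the recordings are deleted straight after transcription, at the end of each study procedure.

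**The concern.** A decision to start sooner because the reading already shows 90% is made while oxygen is climbing. The gap between mask gas and exhaled gas is then wide, so any mask gas in the cannula sample inflates the reading most. After 3 minutes on a sealed circuit the gap has narrowed, and the same contamination inflates the reading much less. A cannula that partly reads mask gas could therefore agree acceptably at every on-oxygen comparison in the NIV arm and still be well above the true value earlier. At stake is whether the trial can say that the cannula tracks exhaled oxygen in real time, or only that it does so at or near its final value.

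**Working it through.** **The plan's own figure.** Power calculation equates 5 points of EtO2 with about 30 s of safe apnea: 0.05 × 2,400 / 250 = 0.48 min = 28.8 s. This reproduces.

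**Inputs.** From Power calculation: store V = 2,400 ml, uptake 250 ml/min, important difference 5 points, SD 6.8 points. From the Precis: NIV FiO2 of 40, 70 and 100%. Not in the documents, so assumed: alveolar ventilation VA = 5 L/min (range 3 to 8), starting value 16%, one well-mixed compartment, and mask-gas share w = 0.5 of the cannula sample.

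**Model.** The steady inspired-to-exhaled gap is 250/VA and the time constant is V/VA. With S = FiO2 − gap, the true value is F(t) = S − (S − 16) × exp(−t × VA/V). The cannula reads c = w × FiO2 + (1 − w) × F, so it over-reads by w × (FiO2 − F).

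Example at VA = 5 and FiO2 100%: gap 5 points, S = 95, time constant 28.8 s.
- 30 s: F = 95 − 79 × exp(−30/28.8) = 67.1; error 0.5 × 32.9 = 16.4.
- 180 s: F = 94.8; error 2.6.

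Over-reading in points, w = 0.5:

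| FiO2 | Time | VA 3 | VA 5 | VA 8 |
|---|---|---|---|---|
| 100% | 30 s | 24.4 | 16.4 | 9.2 |
| 100% | 60 s | 15.0 | 7.4 | 3.0 |
| 100% | 180 s | 5.1 | 2.6 | 1.6 |
| 40% | 30 s | 8.4 | 5.9 | 3.5 |
| 40% | 180 s | 4.3 | 2.5 | 1.6 |

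**At a displayed 90% (FiO2 100%).** The true value is (0.90 − 0.50)/0.50 = 80% at any ventilation. At VA = 5 this occurs at about 48 s (28 to 90 s over VA 8 to 3). By the plan's conversion, 10 points is 0.10 × 2,400 / 250 = 0.96 min, about 58 s of safe apnea.

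**Re-exposure breath (FiO2 100%).** Suppose the earlier maximum counts as regained within 0.5 point of the 180 s reading.
- w = 0.5: the breath falls at 79 to 159 s with an error of 2.1 to 5.6 points (VA 8 to 3), still near the plateau.
- w = 0.75: at VA 4 to 6 it falls at 88 to 123 s with an error of 4.7 to 6.6 points. With a 1-point tolerance it falls at 72 to 102 s with an error of 6.2 to 8.1.

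**Correlation.** Within one trial at fixed FiO2 and constant w, c is a straight line in F with positive slope 1 − w, so Pearson r = 1 whatever the offset. With SD 6.8 halved to 3.4 and 1 point of measurement noise, r = 3.4/√(3.4² + 1²) = 0.96. For the same between-volunteer spread this is equally true on the plateau and on the rise.

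**NRBM arm.** FiO2 is not stated. If the contaminating gas is 100% supply oxygen while room air dilutes the inspired gas to an assumed effective 50 to 95%, then with a 5-point gap the plateau error is 0.5 × (100 − 45) = 27.5 down to 0.5 × (100 − 90) = 5.0 points. Near-convergence need not hold there.

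**The case against.** Comparing near steady state is a defensible choice. At 30 s with VA = 5 the true value moves by (95 − 67.1)/28.8, about 0.97 point per second, so a few seconds between cannula reading and breath would add several points of mismatch. The Introduction's other use, a low reading that prompts delay, is served by a reading after pre-oxygenation, and section 3 (Objectives) asks only how well the two measures correlate. These points stand. They support the present timing for a claim about the final reading, but not for one about the rise.

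A reader might go further and infer that a comparison at 3 minutes is blind to contamination throughout the trial. The documents do not support that. Half of the 104 volunteers are in the NRBM arm, where FiO2 is unstated and an analysis of bias at 3 minutes might expose contamination; flow is also varied there directly (15, 35 and 55 LPM). The re-exposure breath is not tied to 3 minutes and can show errors above 5 points when contamination is heavy. Nor do the large 30 s errors apply to every condition: at 40% FiO2 they are about 3.5 to 8 points.

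It is also tempting to read the mask-gas share straight off an early jump in the trace. At 15 s and 100% FiO2 a perfectly clean cannula has already risen by 0.32 to 0.44 of the distance to FiO2 (VA 4 to 6), so a raw jump would wrongly incriminate it.

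Finally, the plan does not say that the video covers the whole rise, and recordings already transcribed may be gone.

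**Conclusion.** The point holds as a limit on what the trial can conclude. Every cannula/reference pair on oxygen is at the end of 3 minutes or at the cannula's own earlier maximum, and none is scheduled on the rise. In the NIV arm at 100% FiO2 the same half-contaminated cannula would be at or below roughly the plan's 5-point difference at 3 minutes and well above it at 30 s, and the planned correlation would not flag it.

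The size rests on an assumed mask-gas share, ventilation and starting value in a one-compartment model; the documents give none of these. They also give no evidence that the cannula is in fact contaminated, and a reader should not infer that it is. The coefficient named for the primary outcome is not defined. If it were an agreement coefficient it would respond to an offset, but at 3 minutes it would see only the small one. Changing the timing alone would not cure this, because correlation misses constant mixing at any time point; a bias analysis is needed as well.

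**What to change.** 1. Record the elapsed time of the re-exposure breath. Pre-specify the cannula-minus-reference difference, with bias and limits of agreement, at 3 minutes in each condition and at the re-exposure breath, there also plotted against elapsed time.
2. Before the deletion set out under Confidentiality, and where the video covers the rise, transcribe the cannula reading for the first breaths after mask-on and at fixed later times. In the NIV arm, extrapolate the rise back to mask-on to get c(0), and estimate the mask-gas share as (c(0) − room-air reading)/(FiO2 − room-air reading). In the model at 100% FiO2 and w = 0.5, c(0) = 50 + 8 = 58, a jump of 42 points, so the ratio is 42/84 = 0.5; a clean cannula gives 0. Do not use a raw 15 s value. State that this assumes the mask fills quickly and the share is constant.
3. In the Precis/Abstract and Objectives, limit the conclusion to readings at or near the 3-minute or maximal value, and claim no accuracy during the rise.

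Cost: for example, five fixed times in four exposures is 20 extra values per volunteer, plus the first breaths, protocol wording and a narrower conclusion. No participants or procedures are added. Taking the re-exposure breath at a randomised time on the rise would measure the error directly, but it replaces the stated secondary outcome and needs the difference analysis in item 1. It is therefore optional.

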### 3. Introduction and Background:

**Background:** Prior to ED RSI, it is necessary to provide patients with pre-oxygenation to displace nitrogen from the alveoli and replace it with oxygen. This allows the patient to maintain their arterial oxygen saturation during the apneic period of RSI. Patients who experience hypoxia during RSI are at higher risk for serious morbidity and mortality. Techniques commonly employed to pre-oxygenate Emergency Department (ED) patients undergoing RSI include high flow oxygen via a non-rebreather mask (NRBM), a self-inflating bag-valve mask (BVM), or non-invasive ventilation (NIV). However, there are currently no studies that explore how to assess the quality of a patient's pre-oxygenation in real time prior to intubation.

Several recent studies that have assessed the use of single breath end-tidal oxygen to assess the effectiveness of various oxygenation strategies. Typically, healthy volunteers are placed on 2 to 3 minutes of a certain pre-oxygenation strategy followed by exhalation of a single

breath into an end-tidal oxygen sensor. Higher end-tidal oxygen measurements are used as a marker for pre-oxygenation with higher percentages indicating more complete pre-oxygenation.

A goal EtO2 reading of 90% is typically used to indicate maximal pre-oxygenation. However, this method of assessing pre-oxygenation would be impractical in actual ED patients who are critically ill and may not be able to fully participate in such a measurement. In addition, discontinuing a pre-oxygenation method to obtain a single breath EtO2 reading would be unethical as it would interfere with proper pre-oxygenation in a critically ill patient. A better method would be to examine end-tidal oxygen measurements from patients in real-time as they are being pre-oxygenated. This study will examine the use of a real time nasal cannula EtO2 sensor as compared to the gold standard of a single breath exhalation into a static sensor.

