### **3. Objectives:**

Primary Objective: In healthy volunteers, how well does a real time nasal cannula EtO2 sensor correlate with a single breath exhaled EtO2 measurement?

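### The primary outcome is an undefined correlation coefficient; on its usual readings it cannot show a constant cannula offset, and no agreement analysis is planned

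*Combined protocol and SAP*

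**What the plan says.** The primary outcome appears only in section 2 (Precis/Abstract). It is the degree of correlation between the two readings at the end of each 3-minute trial, "as measured by the k correlation coefficient, as measured for each trial". The next sentence continues in the same terms: "The secondary outcome will be the correlation of" EtO2 between the two sensors at maximal readings. Section 3 (Objectives) asks "how well does a real time nasal cannula" sensor correlates with the exhaled breath.

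Other sections describe a comparison of methods. The Background speaks of the cannula "sensor as compared to the gold standard of a single breath exhalation into a static sensor". The Introduction warns that high oxygen flow "could distort patient measurements when placed underneath the oxygen mask", and gives the intended use: if EtO2 "is already at 90% or greater, the clinician may be able to start the intubation procedure sooner".

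The Statistical Analysis section contains a power calculation, an exclusion rule for incomplete participants and a missing-data rule. It names no coefficient, bias estimate, limits of agreement or concordance measure. The power calculation is for a 5% difference in EtO2 with SD 6.8%, six tests at 0.0085 and 52 participants per arm. It does not say which readings are compared.

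On data collection, Study Procedure says that after each treatment "the participant will perform a single breath exhalation into a standard" sensor, and Data collection and storage procedures says that "the study investigators will video record the screens displaying the" EtO2 data.

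**The concern.** A reader cannot tell from the plan which number will be the primary result. The choice matters, because the candidate statistics answer different questions. Pearson and Kendall ask whether people who read higher on one method also read higher on the other. A clinician who compares one reading with 90% needs something else: how far the cannula sits from the reference on average, and how widely individual pairs scatter around that average.

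On the Pearson or Kendall reading, a cannula 5 or 10 points too high at one flow rate would give the same primary result as an unbiased one. The coefficient is calculated trial by trial, so a shift confined to one setting would leave no trace in it. A high coefficient could then be taken as validation although the offset was never reported.

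**Working it through.** **1. The plan's own figures.** Sidak level for six tests: 1 − 0.95^(1/6) = 0.0085, as stated. Dropout: 104/0.90 = 115.6, so 116, as stated. The 52 per arm cannot be matched to a named test because none is named. For 5 points, SD 6.8, two-sided 0.0085 and 80% power, a two-sample t-test needs 47 per arm, Mann-Whitney about 49, and a paired t-test on uncorrelated readings 49 pairs. At 52 pairs the paired t-test has 84% power and Wilcoxon 81%.

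Six tests fits one bias test per trial (three settings in each of two arms). It equally fits three pairwise comparisons of settings within each of two arms. Both are paired comparisons on 52 people, so the power figure cannot decide between them.

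**2. Inputs for the illustration.** From the power calculation: SD 6.8 and 52 pairs per trial. Assumed: the same SD for both methods and all settings, within-pair correlation r, and a constant offset b. The documents give neither r nor b, so ranges are shown.

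**3. Formulas.**
- SD of the paired differences: s = 6.8 × √(2(1 − r)), which is 3.04 at r = 0.90, 4.30 at 0.80 and 6.80 at 0.50.
- Limits of agreement: b ± 1.96s.
- Share of pairs more than 5 points apart: P(Z > (5 − b)/s) + P(Z < (−5 − b)/s).
- Lin's concordance: r / (1 + b²/(2 × 6.8²)). At r = 0.90 this is 0.90/1.270 = 0.71 for b = 5 and 0.90/2.081 = 0.43 for b = 10.
- Kendall for normal data: (2/π) × arcsin(0.90) = 0.71. It does not involve b.

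**4. Results at r = 0.90.**

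| Offset | 0 | +5 | +10 |
|---|---|---|---|
| Pearson | 0.90 | 0.90 | 0.90 |
| Kendall | 0.71 | 0.71 | 0.71 |
| Quadratic-weighted kappa, whole percents (simulated) | 0.89 | 0.70 | 0.42 |
| Lin's concordance | 0.90 | 0.71 | 0.43 |
| Limits of agreement | −6.0 to 6.0 | −1.0 to 11.0 | 4.0 to 16.0 |
| Pairs more than 5 points apart | 10% | 50% | 95% |

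At r = 0.50, Pearson is 0.50 throughout, Lin's is 0.50 / 0.39 / 0.24, and 46% / 57% / 78% of pairs are more than 5 points apart. That Pearson and Kendall do not move with b is an algebraic fact and does not depend on these inputs.

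**5. Why the mean difference alone is not enough.** With no bias and r = 0.50, the limits of agreement are ±1.96 × 6.80 = ±13.3 points. A small mean bias can sit beside wide scatter, so both must be reported.

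**6. Readings at the 90% mark.** With an assumed true mean of 85 and r = 0.90, the cannula shows 90% or more in 7% / 35% / 70% of people truly below 90%, at offsets 0 / +5 / +10 (simulated). These figures cannot describe the 40% and 70% FiO2 trials, where EtO2 near 90% is not attainable. The last figure is also limited by the scale: 23% of simulated cannula readings exceed 100. Capping them brings Pearson down to 0.86.

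**7. Precision with 52 pairs.** The 95% CI half-width for the mean difference is 2.008 × s/√52 = 0.278s: ±0.8 at r = 0.90 and ±1.9 at r = 0.50. For each limit it is 2.008 × s × √(1/52 + 1.96²/(2 × 51)) = 0.479s: ±1.5 and ±3.3.

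**The case against.** - **The plan matches its own objective.** The objective asks about correlation, and the 90% decision is possible future use, not a trial endpoint. Both are true. But that use is the stated rationale, and a statistic blind to offset cannot bear on it.
- ***k* may be kappa.** A weighted kappa would respond to an offset, as the table shows. EtO2 is continuous, though, and without categories or weights kappa cannot be calculated from the plan.
- **The 5% difference may already be a bias test.** It may. The power calculation does not say so or tie the six tests to the primary outcome, so it does not supply the missing analysis. Nor does it show that a bias test was ruled out.
- **Not all distortion is constant.** This stands. Adding independent person-to-person distortion of SD 3 or 5 (assumed) to the cannula lowers r from 0.90 to 0.9 × 6.8/√(6.8² + 3²) = 0.82, or to 0.73. A reader might infer that the primary outcome could not detect any distortion; that goes too far.
- **The pairs may not all exist.** This stands too. The abstract and Study Procedure put a single breath after every intervention. Item #3 under Group 1 and Group 2 has the 3-minute run, a recorded maximum, a rest and a second run, and mentions a single breath only after that second run. A reader might infer that all six trials certainly yield a pair at 3 minutes; the documents do not settle this for the flush-rate and 100% FiO2 trials.
- **Agreement can be calculated later from the same pairs.** Where pairs exist, yes, but a measure chosen after seeing the data carries less weight than a pre-specified one.

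**Conclusion.** The concern holds. The primary statistic is undefined. Its two usual correlation readings ignore a mean shift, its kappa reading cannot be computed, and no agreement analysis is planned. With SD 6.8 per method and r = 0.90, an offset of 5 points puts half of all pairs more than 5 points apart and an offset of 10 puts 95% apart, with no change in Pearson. The size rests on assumed r, offset and equal SDs; the insensitivity to offset does not.

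Two further inferences are not supported. The documents give no evidence that the cannula is in fact biased; the offsets are illustrations. And the failure to reproduce 52 per arm exactly does not show that the sample size is wrong, since the simulated test is not named and 52 exceeds what each of the tests tried needs.

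**What to change.** 1. For each trial, make the primary analysis the mean paired difference (cannula minus single breath) and the 95% limits of agreement, each with confidence intervals. Report them as estimates, without a pass/fail rule. Do the same for the secondary outcome.
2. Replace *k* with a named coefficient as support only, for example Lin's concordance with Pearson's r beside it. Note that it depends on the spread between participants within a setting, so a narrow spread lowers it even when differences are small.
3. State in the power calculation what the six tests compare, and align it with the primary analysis. Use the Sidak-level (99.15%) interval for the mean difference only if those tests are the bias tests.
4. Reconcile the abstract and Study Procedure with item #3 of both groups on whether a single breath is taken at the end of the 3-minute flush-rate and 100% FiO2 runs. If it is not, those two trials have no primary pair and the plan should say so.

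Cost: a formal amendment to the primary outcome, stating whether any paired data have already been examined. The other four trials need no new measurements; the remaining two depend on item 4. The result may look less favourable than a high correlation. With 52 pairs each limit of agreement is estimated to about ±1.5 points at r = 0.90 and ±3.3 at r = 0.50.

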### **Inclusion criteria (with justification in parentheses):**

- Adults 18 years of age and older who are able to consent on their own without a legal representative (ability to consent)
- Self-identified as being in good health (ensuring healthy volunteers)
- Grossly normal dentition as judged by study investigators (may affect NIV mask seal)
- No self-reported symptoms of upper respiratory infection or other infectious process (ensuring healthy volunteers)
- No history of severe pulmonary disease or asthma that requires daily use of an inhaler (ensuring healthy volunteers)
- Females participants only: Self-reported to not be pregnant at time of study enrollment (for protection of an unborn child)

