## **Statistical Analysis:**

## **Power calculation**

The study will be sufficiently powered to detect a 5% difference in ETO2. Five percent was chosen because it equates to approximately 30 extra seconds of safe apnea time in an 80 kilogram male (5% X 2,400 ml/O2 consumption at 250 ml/min). Based on a previous studies with similar study designs, we estimated that the standard deviation of ETO2 would be approximately 6.8%. Because six tests will be conducted, findings will be considered significant at the 0.0085 level (Sidak-corrected p value). These values were used to estimate the sample size required to achieve 80% power using Monte Carlo Simulations (10,000 samples) implemented in R v3.4.1. This analysis returned a total sample size of 104 (52 per arm). In order to account for an anticipated dropout rate of 10%, 116 participants will be enrolled. However, study enrollment will be terminated once 104 study subjects with complete data sets have been enrolled.

If a study participant cannot complete the entire protocol, their data will be excluded from the data analysis.

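### One correlation per fixed setting mixes cannula error with how much volunteers differ, so the main result should be the difference in EtO2 points

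*Combined protocol and SAP*

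**What the plan says.** The objective is broad: "In healthy volunteers, how well does a real time nasal cannula" sensor correlate with a single exhaled breath (section 3, Objectives). It is not limited to any one setting. The Precis/Abstract then states the primary outcome as the correlation at the end of the three-minute period, "as measured by the k correlation coefficient, as measured for each trial". The coefficient called k is not defined.

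The settings are "NRBM at different flow rates (15 LPM, 35 LPM, or Flush rate at 55 LPM") in one arm and "various fractions of inspired oxygen levels (40%, 70% and 100%) for separate trials of 3 minutes at each flow rate" or FiO2 in the other. Each volunteer goes through all settings of the assigned arm, and "participants will be randomized to the order of their treatment sequence" (Study Procedure). Volunteers are "Self-identified as being in good health (ensuring healthy volunteers").

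Under Power calculation, "Because six tests will be conducted, findings will be considered significant at the 0.0085 level (Sidak-corrected p value"). The sample size there rests on a mean difference: "The study will be sufficiently powered to detect a 5% difference in" EtO2, with an SD of about 6.8%. Apart from that calculation and a missing-data rule, the Statistical Analysis section names no analysis. It plans no bias, no limits of agreement, no model that uses the settings together, and no target value for the coefficient.

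**The concern.** Within one setting the flow or FiO2 is the same for everyone, the period is three minutes, and all volunteers are healthy. What remains is the difference between volunteers at that setting plus the error of the two measurements. A correlation measures the first relative to the second. If volunteers are alike at a setting, even an accurate cannula scores low there; if they differ a lot, a poor cannula can score well.

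This bears on the trial's own question. The Introduction raises the possibility that high oxygen flow under the mask disturbs the cannula reading, and six coefficients side by side invite a reader to look for that pattern. A lower coefficient at one flow cannot tell disturbance from uniformity. The use described in the Introduction, judging whether a patient has reached an EtO2 of 90%, depends on the error in EtO2 points, which a correlation does not give.

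**Working it through.** **Inputs from the plan.** Two arms, three settings each, 52 volunteers per arm, six tests at 0.0085, SD of EtO2 about 6.8 points.

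**Assumed inputs, not in the plan.** Error SD e of each sensor; SD s of true EtO2 between volunteers at one setting; mean EtO2 at each setting. Ranges are shown.

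**Step 1. The plan's own figure.** The Sidak level for six tests is 1 − 0.95^(1/6) = 0.00851, so 0.0085 reproduces. Six equals 2 arms × 3 settings, which supports reading the outcome as one coefficient per setting.

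**Step 2. Same cannula, different spread.** With no bias and equal error on both sensors, expected r = s²/(s² + e²).

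| e | s = 1.5 | s = 3 | s = 6.8 |
|---|---|---|---|
| 2 | 2.25/6.25 = 0.36 | 9/13 = 0.69 | 46.24/50.24 = 0.92 |
| 3 | 2.25/11.25 = 0.20 | 9/18 = 0.50 | 46.24/55.24 = 0.84 |

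If the plan's 6.8 is the observed SD, error included, then at e = 2 the value is 1 − 4/46.24 = 0.91. The choice of coefficient does not remove the effect: in simulation at e = 3, as s goes from 2 to 10, Kendall's tau goes from 0.19 to 0.74 and an absolute-agreement ICC from 0.30 to 0.92.

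**Step 3. The order of two cannulas can reverse.** Take single-breath error 2. A cannula with error 1 at s = 1.5 gives 2.25/√(6.25 × 3.25) = 0.50. A cannula with error 5 at s = 6.8 gives 46.24/√(50.24 × 71.24) = 0.77. The worse sensor scores higher.

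**Step 4. The coefficient still responds to the cannula.** At a fixed observed SD of 6.8, r = 1 − e²/46.24, which is 0.98, 0.65 and 0.22 for e = 1, 4 and 6.

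**Step 5. The difference in EtO2 points.** In this model its SD is √(e² + e²) whatever s is. At e = 2 that is 2.83, so the limits of agreement are ±1.96 × 2.83 = ±5.5 points at every setting. With 52 volunteers the 95% CI for the bias is about ±1.96 × 2.83/√52 = ±0.8 points.

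**Step 6. Which summary exposes a bad cannula.** Simulated NIV arm: 52 volunteers, 2,000 runs, assumed means 34/64/93, s = 1.5/3/3, single-breath error 2. Entries separated by slashes are for FiO2 40/70/100%.

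| Cannula | Per-setting r | Within-person slope | Residual SD around slope | Bias by setting | SD of difference |
|---|---|---|---|---|---|
| Unbiased, error 2 | 0.36/0.69/0.69 | 0.995 | 2.8 | 0/0/0 | 2.8 |
| Unbiased, error 8 | 0.11/0.29/0.29 | 0.995 | 8.2 | 0/0/0 | 8.2 |
| Offset 10, error 2 | 0.36/0.69/0.69 | about 1.0 | 2.8 | 10/10/10 | 2.8 |
| Reads delivered gas only (40/70/100), error 2 | 0/0/0 | 1.005 | 3.9 | 6/6/7 | 3.2/4.1/4.1 |

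The slope stays near 1 in all four rows. The per-setting r misses the offset. Bias and SD of the difference, read together, show all three faults.

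A pooled correlation is no better. With assumed means 35/62/88 and observed SD 6.8 it is still 0.93 at e = 6, where the limits of agreement are ±16.6 points.

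**The case against.** Results by setting are a legitimate choice. The Introduction asks whether high flow disturbs the reading, and flow-specific results answer that directly. A coefficient within one setting also shows whether the cannula distinguishes one person from another on the same device; in the gas-only row above it is what falls to zero. This stands, and it is why the coefficients should be kept.

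The low values rest on assumed spreads. The only SD in the plan is 6.8, which gives r of about 0.91 to 0.92 at error 2. This stands too. The documents do not show that volunteers will be alike at any particular setting, nor which settings would score low. They also do not rule it out, and 6.8 is one figure that is not split by setting or into spread and error.

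The plan sets no threshold for the coefficient and states no comparison between settings. That is correct: the risk is a misreading that the outcome invites, not an inference that the plan announces.

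A reader might go further and conclude that the coefficient says nothing about the cannula. Step 4 shows otherwise: it falls as error rises. A reader might also infer that both arms move volunteers across a wide oxygen range that the plan leaves unused, and that a within-person slope should become primary. The documents support the range only for the NIV arm, through its FiO2 levels. The NRBM arm lists flows without expected EtO2 values, and no volunteer is assigned to both arms. Step 6 shows why the slope should not be primary.

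**Conclusion.** The concern holds in this form: a per-setting coefficient responds to cannula error but confounds it with the spread among volunteers, so on its own it cannot say how well the cannula follows the single breath. For one unchanged cannula with error SD 2, the expected value runs from 0.36 to 0.92 as between-person SD goes from 1.5 to 6.8 points.

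The size depends on assumed error SDs, spreads and setting means; the direction does not depend on their exact values. It also rests on reading the outcome as one coefficient per setting, which the wording and the six tests support but do not spell out. The objection that coefficients by setting have a use is accepted; they should not carry the conclusion alone. This is an inexpensive improvement, not a flaw that invalidates the data to be collected.

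**What to change.** - Make the main result the cannula-minus-single-breath difference in EtO2 points. At each setting report the bias and the SD of the difference as 95% limits of agreement, all with confidence intervals.
- Estimate these from a repeated-measures model in each arm, with setting as a factor and a participant effect. Let the variance differ by setting, and base the limits on the total variance (participant plus residual). Note that the SD of the difference contains the error of both methods.
- Define the k coefficient. Keep the six per-setting values as supportive, show each with that setting's single-breath SD, and state that they are not to be compared between settings.
- A within-person slope across settings may be reported as secondary. Neither it nor a correlation pooled over settings should be primary, because differences between settings dominate both.

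The cost is a changed primary outcome and its wording, to be recorded as an amendment, and a little more analysis. No new measurements, visits or participants are needed.
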